#### **4) Inclusion and Exclusion Criteria**

##### **Inclusion Criteria:**

The inclusion criteria for this research study are patients that have been confirmed COVID-19 positive on an acute-care, telemetry-monitored, non-ICU unit and are considered hypoxemic. Hypoxemic is defined as experiencing rising oxygen requirements as evidenced by increasing levels of supplemental oxygen (i.e. starting at 1-2 L nasal cannula and increasing oxygen need from that level, up to 6 L on nasal cannula.) The patient must also be conscious and oriented, as well as able to change positions independently (meaning that it would not take an increased amount of energy or effort to position independently. Subjects will be patients 18 years and older. If the patient is unable to speak, read, or write English, an alternative consent in their language will be utilized.

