##### **Exclusion Criteria:**

The exclusion criteria included those that are not COVID 19 positive. Those patients that are COVID -19 positive and in an ICU setting, or in need of ICU level respiratory treatments and interventions would be excluded, as well as those with respiratory distress (defined as immediate need for intubation, respiratory rate over 35, PaCO2 level above 65, and accessory muscle use) or in hemodynamic instability (systolic blood pressure below 90) or arrhythmia. The researchers would also exclude patients that have agitation or who have altered mental status, unstable spine/thoracic injury or recent abdominal surgery, significant pressure ulcers (above stage 1), pregnant patients past the 2nd trimester, and patients that have concerning neurological issues (such as seizures). Patients that are unable to change positions independently will also be excluded.

*Describe how individuals will be screened for eligibility.*

This is a single-center prospective study which will be conducted over a period of 8 months on a telemetry-monitored, acute care unit in a large tertiary teaching hospital in Houston, Texas. Randomized sampling will be used to recruit and consent 96 patients that meet the study inclusion criteria (48 in the intervention group and 48 in the control group). This study will seek approval from the Common Spirit Health Institutional Review Board, and all participants receiving the intervention will be consented (see consent form attached).

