## **8) Procedures Involved**

**Study Design:** This will be a prospective randomized cohort study in which data will be collected for over 14 days or until discharged or transferred to a lower level of care from the telemetry-monitored, acute care unit. Data collected on study participants will include the need for escalating respiratory care as well as length of stay in the acute care unit. Comparative analysis will be conducted with retrospective data collected from hospitalized patients (the control group) with a diagnosis of COVID-19 on a non-ICU acute care, telemetry-monitored unit that meets the hypoxemia criteria, but that will not receive the proning intervention. The data from the control group will be collected by a retrospective chart analysis after 14 days past their discharge date.

On a confirmed COVID-19 non-ICU acute care, telemetry-monitored unit, there will be two sets of patients: patients that will receive the intervention of proning plus standard of care, and patients that receive standard of care, but not the proning intervention. Confirmed COVID-19 positive patients are randomly assigned by bed control to a room upon admission to the unit. Patients will be randomized upon admission to the acute care, telemetry-monitored unit, and selected based

on inclusion criteria. The patients that will be prone will be identified by a door slot "slider" that is purple. Timing devices will be purchased and placed at the nurses' station, and checklists to indicate proning times will be placed inside the room with a patient identification sticker. The researchers will be following the proning protocol for acute care patients provided by CommonSpirit Health (CSH).

Patients will consent to participation (using an approved consent document from the CSH IRB), and an order for the proning protocol will be entered in the EMR by the physician. The patient will be educated about self-proning, and instructed to self-prone every 2 hours. The nursing staff will document patient position on the checklists every 2 hours.

1. Upon initiation of the initial proning, the patient will be monitored by the RN for adverse effects for 15 minutes (such as inability to tolerate position or signs of respiratory distress).

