2. If the patient tolerates the proning well, the procedure can continue and the RN will set the timer for 2 hours, enter the patient's oxygen saturation into the EMR, and document the position (prone or supine) on the checklist. O2 saturation will be documented at least every 4 hours per unit protocol.
3. The 2 hour timer will be reset each set of 2 hours by the nursing staff, and the intervention will continue until the end of the study period or until the patient is discharged or transferred from that unit.
4. The checklists will be placed in a binder at the nurses' station at the end of each shift and collected daily by a member of the research team.
5. This intervention for each "proned" patient will continue until either of the following occur: either the patient is discharged or transferred to a lower level of care from the acute care floor, or 14 days have passed.
6. A retrospective chart review will be completed by the research team to ascertain length of stay on the acute care, telemetry monitored unit, as well as the need for escalation of respiratory care. Escalation is defined by a need for oxygen requirements above 6 liters of oxygen on the nasal cannula.

*If the patient is assigned to the control group, that patient will receive the standard of care treatment designated by BSLMC policy per their condition on the COVID-19, acute care, telemetry-monitored unit.*

**Data Analysis:** Retrospective data analysis will be conducted by the research team with data collected from the electronic medical record as well as the checklists (oxygen saturation, demographics, proning protocol) for both the interventional and control group. See attached documents for consent/proning protocol documents.

This study will be a prospective cohort study in which data will be collected on subjects for the designated time period. Data will be collected from the electronic medical record as well as the checklists. Data collection will include basic patient demographics, specifically age and gender, height, weight and ethnicity. Clinical data to be collected include O2 saturation, respiratory support methods, proning duration/compliance, presence of hospital acquired pressure injuries,

and need to escalate care to ICU, including initiation of mechanical ventilation. The same data will be collected for the control group - except for proning duration/compliance as they will not receive this intervention.

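### Section 10 calls this a randomized controlled trial, but room placement is the only allocation process described, and patients who decline proning after assignment have no stated place in the data

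*Protocol*

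**What the plan says.** **Allocation.** Section 10 labels the study a randomized controlled trial, with time to discharge from the unit compared between arms as the primary test. Section 8 describes one process: "Confirmed COVID-19 positive patients are randomly assigned by bed control to a room upon admission to the unit". It adds "Patients will be randomized upon admission to the acute care, telemetry-monitored unit, and selected based", the sentence ending with the inclusion criteria. Section 4 says "Randomized sampling will be used to recruit and consent 96 patients that meet the study inclusion criteria". Sections 14 and 15 also speak of random assignment, without a process.

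**Consent.** Section 15 has the team member obtain consent once an intervention patient has been confirmed by random assignment, and Section 14 likewise has the researchers consent patients already assigned. Section 18 describes consent for the intervention group, lets the patient decline the intervention, and requests a waiver for patients assigned to control. Section 4 states that "all participants receiving the intervention will be consented".

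**Data.** Section 9 opens the study record upon consent. Section 8 describes the controls thus: "Comparative analysis will be conducted with retrospective data collected from hospitalized patients (the control group) with a diagnosis of COVID-19", who meet the hypoxemia criteria and will not be proned. Sections 9 and 11 provide for deleting a patient's REDCap profile on request, while Section 11 also says that patients who withdraw are censored on the day of withdrawal.

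**The concern.** A log-rank comparison carries the authority of randomization only if chance formed the arms and the arms are analysed as formed. The protocol secures neither. Room placement by bed control is an administrative act, and nothing shows how a room becomes an arm or whether staff could foresee it.

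After assignment, only one arm passes through a filter. A patient assigned to proning may say no; a comparable control is never asked. If those who refuse tend to stay longer, or shorter, than those who accept, losing them from one arm changes that arm's case mix. Moving them to the other arm changes both. The primary comparison would then mix any effect of proning with the reasons for refusing it.

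**Working it through.** **1. The texts side by side**

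| Question | What the protocol gives |
|---|---|
| Label | Randomized controlled trial (Section 10); prospective randomized cohort (Section 8, Study Design); "This study will be a prospective cohort study in which data will be collected on subjects for the designated time period" (Section 8, Data Analysis) |
| Mechanism | Bed control assigns a room (Section 8); nothing further |
| Who is consented | 96 patients across both groups (Section 4), against a waiver for controls (Section 18) |
| Order | Assignment, then consent (Sections 14 and 15) |
| Decliners | Not stated |

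Two readings of the decliners' fate are open. The record of a consented patient opens upon consent, and the waiver names only patients assigned to control, so decliners may be *left out*. But Section 8 describes controls as hypoxemic patients who will not be proned, so decliners could literally be *moved to control*.

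**2. The plan's own figure**

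Section 10 gives 48 per group for 80% power to detect a 50% shorter time. Under exponential times this is a hazard ratio (HR) of 2. Significance level and event share are not stated; I assume two-sided 0.05.

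- Events needed (Schoenfeld): 4 × (1.960 + 0.842)² / (ln 2)² = 65.3, so 66.
- 66 / 96 = 69%, so 80% power corresponds to about 69% of patients being discharged under observation. If all 96 are, power is 92.4%.

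The figure is attainable but not reproducible from the stated inputs. The present point does not depend on it.

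**3. Illustration of the filter, with no true effect**

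Assumptions, none from the protocol: 40% of patients are slow to be discharged; exponential times; 48 analysed per arm. Follow-up is cut at the protocol's 14 days. Slow and fast patients have ln 2/7 per day times 0.4 and 1.3 (ratio 0.31), or times 0.7 and 1.15 (ratio 0.61). Let *s* and *f* be the refusal rates in slow and fast patients.

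- Slow share among accepters: 0.4(1−s) / [0.4(1−s) + 0.6(1−f)]. With s = 0.4, f = 0.2: 0.24 / 0.72 = 0.333.
- Control share if decliners are dropped: 0.400.
- Control share if decliners are moved: (0.40 + 0.16) / (1 + 0.16 + 0.12) = 0.56 / 1.28 = 0.4375.

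Simulated one-tail error (nominal 2.5%), ratio 0.31 / 0.61:

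| Scenario | False result |
|---|---|
| Equal refusal (20% or 30%), dropped | 2.5–2.7%, no inflation |
| 40% slow, 20% fast, dropped | proning faster: about 5% / 3.5% |
| 40% slow, 20% fast, moved to control | proning faster: about 7% / 4% |
| 50% slow, 10% fast, dropped | proning faster: about 8% / 4.6% |
| 10% slow, 50% fast, dropped | proning slower: about 9% / 4.8% |
| Decliners kept as assigned | 2.6% / 2.6% |

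**4. Price of keeping decliners as assigned**

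Assume HR 2 in accepters, none in decliners, and a 7-day control median. With no refusal, the expected discharges by day 14 are 48 × 0.75 + 48 × 0.9375 = 81, and power is Φ(√81 × 0.693/2 − 1.960) = Φ(1.16) = 88%. Simulation agrees and gives 78% at 10% refusal and 66% at 20%. With 65 per arm (the goal of 130 in Section 15), power at 20% refusal is about 79%.

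**The case against.** - **The protocol says repeatedly that patients are randomized.** True. A reader might infer that no random process exists. The text does not show that; it shows only that none beyond rooming is described.
- **Decliners need not be lost.** A reader might infer that they are certainly excluded. That goes too far. Opening the record upon consent cannot be the general entry rule, since waived controls also enter the data, and Section 18 lets patients decline the intervention, not the study. But the other reading, decliners as controls, is no better.
- **Consent after assignment in one arm is a recognised design** (Zelen single consent). It is, and the analysis set might be left to an SAP. The assignment mechanism and the capture of decliners' data belong in the protocol.
- **The bias is hypothetical and modest.** Refusal rates and prognosis gaps are assumed. Total two-sided error at 40%/20% refusal with decliners dropped is only about 6% against 5%. This stands: the figures show that bias is possible, not that it is expected, nor that it favours proning.
- **Section 4 does not contradict itself on consent.** Correct. Its sentence on those receiving the intervention does not say that nobody else is consented. The conflict is between Section 4 and the waiver in Section 18.
- **The controls need not be historical.** The word retrospective in Section 8 may mean only later chart extraction. The same section says of the proned patients' procedures that "A retrospective chart review will be completed by the research team to ascertain length of stay". The text does not settle it.

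**Conclusion.** The concern holds in this form: the randomized label is not backed by a described allocation process, and a post-assignment refusal step in one arm is left without a rule for those who refuse. On either open reading, the primary comparison is not between the groups as assigned. Size and direction of bias cannot be derived from the protocol, and it is nil if decliners have the accepters' prognosis. The importance of the point rests on the unverifiable randomization and the one-sided filter, not on the simulated percentages. It needs settling before enrolment, because arms that were not formed by chance, or decliners who were not recorded, cannot be recovered later.

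Two matters are minor. Whether eligibility precedes assignment is unclear: Section 4 samples eligible patients, Section 8 randomizes on admission, and "Hypoxemic is defined as experiencing rising oxygen requirements as evidenced by increasing levels of supplemental oxygen", which may appear only after admission. The differing design labels are editorial.

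**What to change.** 1. In Section 8, state that eligibility is confirmed and recorded first, and that a concealed, computer-generated 1:1 assignment independent of rooming (for example from the REDCap system already in use) is then released.
2. Enter every patient in REDCap at assignment. Ask the IRB to let the waiver cover record data of patients who decline proning. Analyse all assigned eligible patients in their assigned arm, never decliners as controls.
3. Reconcile the profile deletion in Sections 9 and 11 with censoring on the withdrawal day in Section 11. Deletion is triggered by the patient, and withdrawal is explained during consent (Section 17), so it reaches essentially the proning arm only.
4. Restate the 80% power in Section 10 with the expected refusal. By the figures above, 48 per arm falls below 80% at 10% refusal, and the goal of 130 gives about 79% at 20%.
5. Reconcile Section 4 with the waiver, use one design label, and have the sponsor clarify whether the controls are concurrent patients whose charts are extracted later.

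**Alternative:** consent both arms before assignment. This removes the one-sided filter but costs about 48 × 15 minutes = 12 staff hours and exposes controls to the proning teaching, while proning is not recorded for them. If 10% or 20% of controls self-prone with full effect, power at 48 per arm is about 81% or 72% under the same assumptions.

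**If rooming is the only mechanism:** drop the randomized label and plan an adjusted non-randomized comparison.

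**Cost:** a protocol and IRB amendment, an assignment procedure, and probably more patients than the minimum of 96, when Section 15 calls recruitment feasibility unknown.

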## **14) Setting**

The research study will be conducted in St. Luke's Health - Baylor St. Luke's Medical Center - Houston, TX (address: [name]), in a telemetry-monitored, acute care unit for covid-positive patients. The researchers will consent randomly assigned patients from that unit, and the intervention will be contained to that unit.

The study is being propagated by BSLMC's Nursing Research and Education Council after having been approved by the CNO, and is being submitted for review by the CSH Institutional Review Board. After approval, the study will be commenced.

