- Once each intervention patient is confirmed via random assignment, the research team member assigned that day will meet with the nurse assigned to the

intervention patient. The research team member will obtain consent from the patient. That team member will assess if the nurse needs help monitoring the patient for the initial 15 minutes of proning, and assist as needed.

- That team member will also educate the nurse assigned as to how often proning occurs (every 2 hours), to document patient position on the checklist every two hours, the proning protocol, and where to put the checklist at the end of their shift. The team member will leave upon confirmation of correct implementation of the study.
- The checklists from the intervention patients will end up in a binder at the end of the shift, and the binder will be emptied at that time by a member of the research team. These checklists' data will be entered into the computer by the research team, kept until the end of data collection period in a locked filing cabinet, and then destroyed at the end of the data collection period.

The resources for the patient should there be more than minimal harm caused include the medical resources of our facility.

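### Section 8 randomises on unit admission and selects on the inclusion criteria without concealment, so eligibility can be judged with the arm already known

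*Protocol*

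**What the plan says.** **Assignment.** Section 8 (Study Design) says "Confirmed COVID-19 positive patients are randomly assigned by bed control to a room upon admission to the unit". The next step reads "Patients will be randomized upon admission to the acute care, telemetry-monitored unit, and selected", and the sentence goes on to name the inclusion criteria as the basis of selection.

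**Eligibility.** Section 4 sets two criteria that matter here. The first is a trend: "Hypoxemic is defined as experiencing rising oxygen requirements as evidenced by increasing levels of supplemental oxygen", starting at 1-2 L and going up to 6 L by nasal cannula. The second is being able to change position unaided, explained as "meaning that it would not take an increased amount of energy or effort to position independently". The screening text in the same section says "Randomized sampling will be used to recruit and consent 96 patients that meet the study inclusion criteria".

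**Contact and consent.** Section 14 says "The researchers will consent randomly assigned patients from that unit". Section 15 says "Once each intervention patient is confirmed via random assignment, the research team member assigned that day will meet with the nurse", and consent is obtained after that. Section 18 describes bedside consent for patients already assigned to proning, who may decline, and a waiver for controls.

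**Visibility.** Proned patients are marked by a purple door slider and by checklists in the room (Section 8).

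**The concern.** The log-rank comparison in Section 10 relies on randomisation to balance the patients who are analysed. That holds if the analysed set is fixed by assignment, or by facts settled before anyone knew the assignment. In this plan the assignment is made at the unit door, while membership of the analysed set depends on a trend that may appear later and on a bedside judgement. Both are plausibly related to severity, and severity plausibly drives time to discharge.

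If the people judging eligibility know the arm, they can apply the criteria differently by arm without intending to. A patient for whom turning is tiring is more likely to be queried when turning is what the arm requires. Patients assigned on admission and then not selected fall outside the 96, and the protocol asks for no record of them, so a later reader could not see whether selection differed by arm.

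**Working it through.** **1. The order, from the text.**

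| Step | Where | Timing |
|---|---|---|
| Room allocation by bed control | Section 8 | On unit admission, all confirmed positive patients |
| Randomisation | Section 8 | On unit admission |
| Selection on criteria | Section 8 | Joined to randomisation by *and*; no time given |
| Rising oxygen need | Section 4 | A trend, so it may appear after admission |
| Research contact and consent, prone arm | Sections 14, 15, 18 | After assignment |
| Concealed list, or eligibility fixed before the arm is known | None | Not described |

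The sequence of assignment followed by selection is an inference, but a well-supported one. Assignment is tied to admission, one criterion may not be met until later, and every later contact in the prone arm starts from a known assignment.

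**2. The plan's own figure.** Section 10 claims 80% power with 48 per group for a 50% decline in time to discharge. Assume exponential times (discharge hazard ratio 2) and two-sided alpha 0.05; neither is stated.
- Schoenfeld: 4(1.96 + 0.842)² / (ln 2)² = 31.4 / 0.480 ≈ 65.4, so 66 events, and 66/96 = 69%.
- Freedman: (1.96 + 0.842)² × (3/1)² = 7.85 × 9 ≈ 70.7, so 71 events, and 71/96 = 74%.

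The 80% is attainable if about 69% to 74% of patients are discharged within follow-up. The present point does not depend on this figure and does not change it.

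**3. Size of a one-arm worst case.** None of these inputs is in the protocol except 48 per arm, the log-rank test and the 14-day horizon. Severity s is N(0,1). The discharge hazard is (ln 2 / 8) × exp(−0.8 s), so the median is 8 days at average severity. Judged severity is s plus noise of SD 0.5 or 1.0. There is no true effect. The sickest fraction, as judged, is removed from the prone arm and replaced; controls are left unselected. There were 4,000 trials per setting.

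| Removed from prone arm | False result favouring proning, noise SD 0.5 | Noise SD 1.0 | Apparent discharge rate ratio |
|---|---|---|---|
| 0% | 2.2% | 2.8% | 0.99-1.01 |
| 10% | 6.8% | 5.4% | 1.09-1.10 |
| 20% | 12.2% | 9.8% | 1.17-1.22 |
| 30% | 23.9% | 16.1% | 1.26-1.35 |

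Nominal is 2.5% one-sided. Repeat runs agree within about 2 percentage points.

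**4. Other patterns in the same model.**
- Same filter in both arms at 10%, 20% or 30%: 2.4% to 2.7%, which is nominal.
- 20% removed from prone against 10% from control, or 30% against 20%: about 5% to 6%.
- Healthiest 10% to 20% removed from the prone arm only: false results favouring proning fall to 0.2% to 1.1%, and false results against it rise to about 5% to 12%.

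**5. A second model.** Half the patients are slow to discharge, the good-versus-poor discharge hazard ratio is 2 to 4, the median is about 7 days, and 10,000 runs were made per setting. Removing 20%, 40% or 60% of the poor-prognosis patients from the prone arm only gives two-sided error of about 6%, 6% to 11% and 10% to 21%, against about 5% with none removed. As the share removed rises, nearly all the false positives favour proning. Removing 20% of the poor half means 0.20 × 0.50 = 10% of all patients, so the fractions here are not on the same scale as in step 3.

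**The case against.** **The order is not stated outright.** The word *and* sets no sequence, and no section says who judges eligibility or when. This stands: a reader might infer that the protocol prescribes eligibility decisions after assignment, or gives ward nurses that decision, and it does neither. What remains is that assignment is placed at admission, nothing requires eligibility to be settled first, and nothing hides the arm.

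**Section 4 does not contradict Section 8.** It speaks of recruiting patients who meet the criteria, without placing that step before assignment. It is open to either reading, so it neither proves nor cures the problem.

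**Order alone does not produce bias.** This also stands. With the same filter in both arms the error rate is nominal. Controls must meet the hypoxemia criteria too (Section 8), so a screen acting on the prone arm only is a worst case. The order supplies the opportunity; uneven application supplies the bias.

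**The direction is not established.** A reader might infer that the result would favour proning. The documents do not support that: staff could as easily steer sicker patients into proning, or bring them in later once oxygen need has risen, and the bias would then run the other way.

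**Overlap.** One-arm consent and controls taken from charts after discharge are separate problems that also select after assignment. The figures above should not be added to any estimate for those. Equalising consent alone would not remove this point, because the arm would still be known when eligibility is judged.

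**Conclusion.** The point holds as a defect in the design as written: in an open trial the plan assigns at admission, leaves later-developing and judgement-based criteria to be applied with the arm known, and requires no count of patients assigned but not selected. An analysis plan could not repair this, because the patients lost between assignment and selection are not recorded.

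It is an opportunity for selection bias, not evidence that bias will occur. The figure of about 5% to 24%, against 2.5% nominal, is the one-arm worst case for removal of the sickest 10% to 30%. It rests on an assumed median, severity spread and judgement noise, and its upper end needs 30% of one arm removed and none of the other. A 10-point difference in screening between arms gives about 5% to 6%. No figure in the protocol says which of these, or which direction, to expect. The change should be made because it is cheap and closes the route whatever its size.

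**What to change.** In Section 8, delete randomisation on admission and state that room allocation by bed control does not determine the arm. Replace it with wording to this effect:

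> Every candidate, whichever arm may follow, is screened on the unit with the same form and the Section 4 criteria. When all criteria are met, a research team member locks a dated eligibility form in REDCap. The consent step, in the form the IRB approves, is completed before the arm is revealed. Only then is the arm revealed, from a pre-generated REDCap list that screeners and unit staff cannot see. All assigned patients are analysed in their assigned arm from the date of assignment, including those who decline proning, as far as consent and data-withdrawal rules allow. Anyone removed after assignment is counted by arm.

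Bring the other sections into line with this order: the screening text in Section 4, deletion of a withdrawn patient's data in Sections 9 and 11, consent of assigned patients in Section 14, the daily workflow in Section 15, and consent and waiver in Section 18. The consent change needs IRB agreement.

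**Cost.** A protocol amendment across these sections, one eligibility form and a concealed list in the REDCap system already in use. A research team member already attends the unit daily (Section 15). Assignment happens somewhat later than admission, and control candidates must be screened prospectively on the same form, which is more work than identifying them from charts. N = 96 and the power statement do not change.
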